## **6.4 Serious adverse event reporting**

To ensure patient safety, **every SAE**, regardless of suspected causality, occurring after the patient has provided informed consent and until 30 days after the patient has stopped study participation (defined as time of last dose of ranibizumab taken during the study or last visit whichever is later) **must be reported to the Sponsor within 24 hours of learning of its occurrence**. Any SAEs experienced after this 30 day period should only be reported to the Sponsor if the investigator suspects a causal relationship to ranibizumab. Information about all SAEs is collected and recorded on the Serious Adverse Event Report Form. The investigator must assess the relationship of any SAE to ranibizumab, complete the SAE Report Form in English and send by fax or e-mail the completed, signed form within 24 hours of learning of its occurrence to Sponsor. The original copy of the SAE Report Form and the fax confirmation sheet or email receipt confirmation must be kept with the case report form documentation at the study site. A SAE that is considered completely unrelated to a previously reported one should be reported separately as a new event.

The outcome of all reported SAEs (resolution, death etc.) will be followed up and documented. Recurrent episodes, complications or progression of the initial SAE must be reported as follow-up to the original episode, regardless of when the event occurs. Follow-up information is sent within 24 hours of the investigator receiving the follow-up information using a new SAE Report Form stating that this is a follow-up to the previously reported SAE and giving the date of the original report. The follow-up information should describe whether the event has resolved or continues, if and how it was treated, and whether the patient continued or withdrew from study participation.

If the SAE is unexpected, i.e. not previously documented in the local product SPC and is thought to be related to ranibizumab, the Sponsor may urgently require further information from the investigator for Health Authority reporting.

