
**CONFIDENTIAL**

This document is confidential and the property of individual. No part of it may be transmitted, reproduced, published, or used by other persons without prior written authorization from the author.

[figure not shown]

Safety assessments:
	
All Serious Adverse Events (SAEs) reported to or noted by the physician from the time the patient signs the informed consent until 30 days after study discontinuation will be recorded in the SAE Case Report Form (CRF) and reported to the Sponsor within 24 hours of learning of its occurrence. All Adverse Events (AEs) will be captured on the AE CRF throughout the safety recording period (see Section 6 for details). AEs detected through ophthalmic examinations will be collected if available.

Clinical assessments and data collection:
	
Timing of actual patient visits is at the discretion of the treating physician. It is recommended all visits should be documented in the CRF within 1 month post visit. A minimum of three visits per year is required in order to maintain a patient's participation in the study.
 
Data elements to be collected include demographics and medical history/ocular history (baseline only), relevant prior and concomitant medications, ophthalmologic examination, treatment information, VA, CRT as evaluated with Optical Coherence Tomography (OCT), SAEs/AEs.
 
Physicians will be encouraged to follow-up with patients who have not been seen in the clinic for at least 3 months since the last visit to capture any AEs/SAEs that may have occurred since the previous visit, and again 3 months later if no subsequent visit occurs within the following 3 months.

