## 2.2 Secondary Objectives

- To evaluate the safety of ranibizumab as assessed by the type, frequency and severity of ocular and non-ocular AEs over 12 months of treatment with intravitreal injections of ranibizumab for the treatment of neovascular AMD in treatment naive patients in routine clinical practice in Greece.
- To describe treatment patterns of ranibizumab administration for neovascular AMD in routine clinical practice in Greece.
- To evaluate the anatomic effectiveness of ranibizumab treatment of neovascular in treatment naive patients with neovascular AMD in routine clinical practice in Greece as observed in this 1-year study duration and assessed by mean change in CRT from baseline to month 12.

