## 6.1 Adverse event

An AE is the appearance of any sign(s), symptom(s), or medical condition(s) or the worsening of any pre-existing undesirable sign(s), symptom(s), or medical condition(s) occurring after signing the informed consent during the safety recording period even if the event is not considered to be related to ranibizumab.

The occurrence of AEs should be sought by non directive questioning of the patient at each visit during the study. Adverse events also may be detected when they are volunteered by the patient during or between visits or through physical examination, laboratory test, or other assessments provided by the patient. Clinically significant abnormal laboratory values or test results should be identified through a review of values outside of normal ranges or clinically notable ranges, significant changes from Baseline or the previous visit, or values which are considered to be non-typical in patient with underlying disease. Investigators have the responsibility for managing the safety of an individual patient and identifying clinically significant AEs.

Once an AE is detected, it should be followed until its resolution or until it is judged to be permanent, and assessment should be made at each routine visit (or more frequently, if necessary) of any changes in severity, the suspected relationship to ranibizumab, the interventions required to treat it, and the outcome.

Physicians will be encouraged to follow-up with patients who have not been seen in the clinic for at least 3 months since the last visit to capture any AEs that may have occurred since the previous visit, and again 3 months later if no subsequent visit occurs within the following 3 months.

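### For a patient who does not return, Section 6.4 ends causality-independent SAE reporting 30 days after the last dose or visit, before the encouraged 3-month contacts and possibly well inside the 12-month safety period

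*Protocol*

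**What the plan says.** Section 6.4 requires every SAE, whatever its cause, to reach the Sponsor within 24 hours if it occurs after consent and "until 30 days after the patient has stopped study participation". It then defines that end point: "defined as time of last dose of ranibizumab taken during the study or last visit whichever is later". Beyond it the rule narrows: "Any SAEs experienced after this 30 day period should only be reported to the Sponsor if the investigator suspects a causal relationship to ranibizumab".

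Other parts of the protocol bear on the same window:

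- **Synopsis, Safety assessments.** SAEs that come to the treating doctor's attention "from the time the patient signs the informed consent until 30 days after study discontinuation will be recorded in the SAE Case Report Form" and sent to the Sponsor. Discontinuation is not tied to the last dose or visit.
- **Synopsis, Clinical assessments, and Section 6.1.** Physicians are encouraged to follow up patients unseen for "at least 3 months since the last visit to capture any AEs/SAEs that may have occurred since the previous visit" (synopsis wording; Section 6.1 mentions AEs only), with a second contact 3 months later if there is still no visit. Section 5 has the first contact only, to collect the Table 5-1 items, which include SAEs and AEs.
- **Section 6, opening.** The safety recording period starts after consent. No end is given there or in 6.1 to 6.5.
- **Section 6.2.** All AEs in that period are recorded irrespective of causality, with a field for seriousness.
- **Sections 4.4, 4.4.2 and 5.** Withdrawal, loss to follow-up and discontinuation for too few visits are determinations made after visits have been missed. Section 5.4 has no withdrawal visit.
- **Section 2.2.** The safety objective covers "type, frequency and severity of ocular and non-ocular AEs over 12 months of treatment".

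**The concern.** The study has no preset visit schedule, and three visits a year, counting baseline and end of study, keep a patient in. Gaps of several months are therefore permitted. If a patient has a serious event in such a gap and never attends again, the last visit stays where it was, and the 30-day limit may already have passed when the event occurs. If the investigator does not suspect ranibizumab, Section 6.4 as written does not make the event reportable, even at month 6 of a 12-month safety period.

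The missing events would not be a random subset, because the event itself may be what stops attendance. The serious systemic events named in the background section (myocardial infarction, stroke, vascular death) are of this kind. Section 8.1 keeps enrolled patients in the secondary analyses whether or not they complete, and Section 8.4.1 tabulates the proportion with any serious AE. A non-returning patient can therefore stay in the denominator while the event never enters the numerator.

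**Working it through.** The protocol gives no figure of its own on this point, so there is none to reproduce. The check sets the dates side by side and then finds what share of a gap lies outside the window.

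**Dates for a patient who does not return.** Let L be the later of last dose and last visit, and D the date on which discontinuation is determined.

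- Section 6.4 window closes at L + 30 days.
- First encouraged contact: about L + 91 days, which is 91 − 30 = 61 days after the window has closed.
- Second encouraged contact (synopsis and Section 6.1): about L + 182.5 days, which is 182.5 − 30 = 152.5 days after it has closed.
- Synopsis window, with discontinuation read as a later determination: D + 30 days. The two windows differ by (D + 30) − (L + 30) = D − L. With a last visit at month 4 and discontinuation determined only at month 12, they end at about months 5 and 13, or 12 − 4 = 8 months apart. That is a deliberately long case. The difference shrinks if the site determines the loss sooner.

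**Share of a gap outside the window.** Assume the event that prevents return is equally likely on any day of a gap of g days after L. The share outside is max(0, g − 30)/g.

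- 4 weeks: g = 28, share 0%.
- 8 weeks: 26/56 = 46%.
- 12 weeks: 54/84 = 64%.
- Up to the first contact, about 3 months: 61/91 = 67%.
- Up to the second contact, or an evenly spaced three-visit year: 152.5/182.5 = 84%.
- Visits at day 0 and about day 30, then none until month 12: g = 365 − 30 = 335, share 305/335 = 91%.

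The complement is covered: in a 91-day gap, 30/91 = 33% of event times fall inside the window. The longer gaps are patterns the protocol permits. It gives no actual visit intervals, so they should not be read as expected patterns.

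**Whether another rule catches the event.** Section 5 and the footnote to Table 5-1 say that SAEs learned of outside a visit must be reported, but according to Section 6.4, which leads back to the same window. Section 6.2 would record the event on the AE form if it falls in the safety recording period, but that period has no stated end. Neither provision settles the matter.

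**The case against.** The strongest reply is that Section 6.4 governs what is sent to the Sponsor, while Section 6.2 separately requires AEs to be recorded whatever their cause. Section 6.4 itself says that information on all SAEs is collected on the SAE form, and Section 8.4.1 does not restrict the safety tables to SAEs reported under 6.4. This stands in part: loss from the tables is possible but not shown. It does not clear the plan, because Section 6.2 works only within a period whose end is missing, and the synopsis puts recording and reporting of SAEs in one sentence with one window.

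A second reply is that study discontinuation in the synopsis is undefined, so the bracket in 6.4 could serve as its definition. That reading is possible, but it sits badly with Sections 4.4, 4.4.2 and 5, where discontinuation follows missed visits. Relatedly, a site cannot know at day 31 which visit will prove to be the last, so many sites would probably report anyway. That makes the literal rule hard to apply, but it does not make it right.

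Two stronger readings are tempting and not supported:

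- A reader might infer that all strokes, infarctions and deaths that stop attendance fall outside the window. They do not. Events within 30 days of the last dose or visit are inside it, events suspected to be related stay reportable without limit, and any later visit moves the window to cover the earlier event. With visits about every 4 weeks, nothing is lost.
- A reader might halve the 2-year arterial thromboembolic rates in the background section (4.6%/2 × 251 = 5.8; 5.0%/2 × 251 = 6.3, so about 6 events in a year) and conclude that one or two would go unreported. That needs a constant hazard, transfer from phase III trial patients, a guessed proportion who never return, and 3-month gaps. The protocol supports none of these, and the range starts at zero.

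It is also true that the contacts are encouraged, not required, and that Section 5 contains only the first.

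**Conclusion.** The point holds as an inconsistency in the safety reporting rules. Followed as written, Section 6.4 makes some serious events within the 12-month safety objective non-reportable: those in patients who do not return, more than 30 days after the last dose or visit, and not suspected to be related. This conflicts with contacts meant "to capture any AEs that may have occurred since the previous visit" and fits poorly with the synopsis window. Because the recording period has no stated end, capture by another route is not assured, and such events may be under-counted.

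The share of a gap outside the window ranges from 0% at about 30 days to about 67% at 3 months and about 84% at 6 months. It rests on a uniform event time and applies only to events that prevent return. No count of lost events can be derived from the protocol, and it may be zero. The point should still be corrected, because it is a stated rule that works against the objective, and not merely a missing detail.

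**What to change.** Reconcile the synopsis (Safety assessments and Clinical assessments), the opening of Section 6, and Sections 6.1, 6.2 and 6.4 on one stated end for the AE recording period and one for the SAE window. Neither should be set by the last attendance of a patient who does not return, and neither should be shorter than the present rule for completers. The end-of-study visit may fall up to 7 days after the month-12 date, so that date alone would not do.

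One workable form: SAEs are reported until 30 days after the later of the month-12 date and the end-of-study visit. For earlier exits, the end is tied to death, consent withdrawal or documented discontinuation. The date of the discontinuation decision should be recorded, so that the window does not depend on when a form is completed. State that SAEs within the window that are learned of at the encouraged contacts are reported regardless of causality and counted in the safety tables. Align Section 5 with the synopsis and Section 6.1 on whether there is a second contact.

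The cost is protocol wording, matching SAE form instructions and a few more SAE reports to process. No visit or procedure is added.

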## **6.5 Pregnancies**

A female patient must be instructed to stop taking ranibizumab if she becomes or intends to become pregnant during the study.

To ensure patient safety, all pregnancy cases in patients treated with ranibizumab must be recorded on a Clinical Trial Pregnancy Form and reported by the investigator to the Sponsor within 24 hours of learning of their occurrence. The pregnancy should be followed up to determine outcome, including spontaneous or voluntary termination, details of the birth, and the presence or absence of any birth defects, congenital abnormalities, or maternal or newborn complications. Pregnancy follow-up should be recorded on the same form and should include an assessment of the possible relationship to ranibizumab of any pregnancy outcome.

Any SAE experienced during pregnancy must be reported on the Serious Adverse Event Report Form; see Sections 6.3 and 6.4.

## **7 Data review and database management**

All activities described in this section will be performed by the CRO on behalf of the Sponsor. A CRO will be selected and assigned for the Electronic Data Capture (EDC) system development. The electronic CRFs will be part of the EDC system which allows documentation of all outcome variables and covariates by all participating sites in a standardized way.

Details of clinical site monitoring will be documented in a Clinical Monitoring Plan (CMP) developed by the CRO contractor.

### **7.1 Site monitoring**

Clinical site monitoring is conducted to ensure that the rights of human subjects are protected, that the study is implemented in compliance with the protocol and in accordance with the International Conference on Harmonisation (ICH) guidelines for Good Clinical Practice (GCP), with the ethical principles laid down in the Declaration of Helsinki, with the Greek National Organization of Medicines (EOF) regulations and that the quality and integrity of study data and data collection methods are maintained. All visits according to CMP will take place at the study sites.

#### **CONFIDENTIAL**

This document is confidential and the property of individual. No part of it may be transmitted, reproduced, published, or used by other persons without prior written authorization from the author.

Before study initiation, at a site initiation visit, the CRO representative will review the protocol and CRFs with the investigators and their staff. Entrance of data to the electronic CRFs will be conducted by the treating investigator or by a designated person. During the study, the field monitor may visit the site according to the CMP, to evaluate study processes, check the completeness of patient records, the accuracy of entries on the electronic CRFs, the adherence to the protocol, to ICH guidelines for GCP, to the ethical principles laid down in the Declaration of Helsinki and to the EOF regulations. Documentation of SAEs and the progress of enrollment will be also evaluated. Key study personnel must be available to assist the field monitor during these visits.

The investigator must maintain source documents for each patient in the study, consisting of case and visit notes (hospital or clinic medical records) containing demographic and medical information, laboratory data, and the results of any other tests or assessments. All information on electronic CRFs must be traceable to these source documents in the patient's file. The investigator must also keep the original informed consent form signed by the patient (a signed copy is given to the patient). The investigator must give the monitor access to all relevant source documents to confirm their consistency with the electronic CRF entries. Checks of the consistency of the source data with the electronic CRFs are performed according to the study-specific CMP. No information in source documents about the identity of the patients will be disclosed.

Staff from the CRO contractor will conduct monitoring activities and provide reports of the findings and associated action items in accordance with the details described in the CMP. Documentation of monitoring activities and findings will be provided to the Sponsor, the site study team and the study PIs. The Sponsor reserves the right to conduct independent audits as necessary. The observations and findings of an audit should be documented.

## **7.2 Data collection**

Sites are required to enter study information in electronic CRFs. Designated investigator staff will enter the data required by the protocol into the electronic CRFs after appropriate training.

Automatic validation programs check for data discrepancies and, by generating appropriate error messages, allow the data to be confirmed or corrected before transfer of the data to the CRO. The Investigator must certify that the data entered into the electronic CRFs are complete and accurate.

### 7.3 Data management and quality control

The CRO working on behalf of the Sponsor will review the data entered into the electronic CRFs by investigational staff for completeness and accuracy and instruct the site personnel to make any required corrections or additions. Queries are sent to the investigational site using an electronic data query. Designated investigator site staff is required to respond to the query and confirm or correct the data.

### 7.4 Planned database locks

No interim analyses are planned in the study. Consequently, there will be no other database lock (DBL) than the final DBL.

## 8 Data Analysis

The statistical section below describes analyses as planned for the study. The statistical analyses will be performed by the designated CRO.

The study is not aimed to confirm or reject pre-defined hypotheses.

Continuous variables will be summarized with the use of descriptive statistical measures (mean value, standard deviation, median, minimum and maximum values) and categorical/distinct variables will be displayed as frequency tables (N, %).

If applicable, the analyses will be stratified by baseline factors. Baseline patient characteristics that may be used for subgroup analyses, providing that the number of patients per subgroup allow for meaningful inferences, include but are not limited to the following: age, smoking status, concomitant diseases, type of CNV etc.

The study eye will be defined as the eye for which treatment with ranibizumab is initiated and analyses will be done for the study eye only.

The analysis of adverse events will be based on observed data.

Complete analytical specifications will be fully detailed in the statistical analysis plan (SAP). The SAP will be finalized before study DBL and will specify any performed analyses that will be stratified for baseline factors.

#### **CONFIDENTIAL**

This document is confidential and the property of individual. No part of it may be transmitted, reproduced, published, or used by other persons without prior written authorization from the author.

A level of  $p < 0.05$  will be considered to be statistically significant.

## **8.1 Analysis sets**

The enrolled set will include all patients having signed the informed consent, and with at least a baseline assessment.

The Per Protocol Set will consist of all patients who complete the study without any major protocol deviations.

The study eye set will include all study eyes treated with ranibizumab.

In accordance to the non-interventional design of the study, all statistical analyses with the exception of the primary objective will be performed in all eligible subjects with available data who have been enrolled into the study, regardless of whether or not they have finally completed their projected participation in the study.

## **8.2 Patient demographics and other baseline characteristics**

Descriptive statistics will be provided for patient demographics and all baseline characteristics (including the baseline values of the primary and secondary efficacy variables). Relevant medical history (ocular and non-ocular), current medical conditions will be tabulated by site (non-ocular, ocular (study/fellow eye)). Other relevant baseline information like tobacco use will be listed and summarized as appropriate with descriptive statistics.

Statistical analyses will be based on the enrolled set.

